1b. Determine whether patients with aphasia learn the strategy and consequently demonstrate a change in their language behavior in moments of naming difficulty. Hypothesis: We hypothesize that strategy training will lead PWA to correctly identify the strategy's components post-treatment. We also hypothesize that strategy training will lead PWA to produce more feature words (i.e., engage in circumlocution) during moments of naming difficulty. Specifically, we expect to find medium to large effects on the number of feature words PWA produce during naming attempts post-treatment.

Aim 2. Evaluate the effect of strategy training on patients' language production during connected speech. Approach: We will collect and transcribe connected speech samples, including spoken descriptions of pictures, weekly activities, and personal memories⁷³, pre- and post-treatment. Hypothesis: We hypothesize that strategy training will lead PWA to produce more object and feature words during connected speech. We expect medium to large effects on object words, feature words, and measures of communicative effectiveness⁶⁴.

III. SUBJECT SELECTION

a. Inclusion/exclusion criteria.

Eligible individuals will:

- Experienced a single left-hemisphere stroke,
- Have aphasia due to stroke,
- Be in the chronic stages of their aphasia, at least 6 months post onset of stroke,
- Be between the ages of 18 and 89 years of age, and
- Be a proficient English speaker,
- Have no history of neurodegenerative disease, severe motor speech disorder, significant mental illness, psychiatric disorder, drug/alcohol abuse, or neurological condition that could influence their cognitive, language, and memory systems.

Participants may have concomitant medical problems such as heart disease or diabetes; however, at the time of their participation they will be medically and neurologically stable and at least wheelchair ambulatory.

Participants with a history of minor head injury or short-term loss of consciousness are eligible to participate, however a brief history of these instances will be obtained in order to control for potential secondary impacts to learning and memory systems. Similarly, history of developmental learning disorders will be obtained, as this can affect learning and strategy development/compensatory systems, which are a focus of our research study.

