Phase 4 post-treatment tests of retention: Participants will attend two additional post-treatment sessions one month and two months after treatment completion to evaluate retention. During these study visits, participants will complete naming assessment and a connected speech connected speech task in which we will ask participants to verbally describe a picture, weekly activity, or personal memory description (e.g., *Tell me all about your weekend*).

- b. Drugs to be used: N/A
- c. Devices to be used: N/A
- d. Procedures/surgical interventions: N/A

e. Data to be collected and when data is to be collected

Pre- and post-treatment data: All pre-treatment and post-treatment cognitive-linguistic assessment data will be collected during pre- and post-treatment assessment sessions. This data will be collected on each respective assessment material's proper test booklet. Data from pre- and post-treatment naming probes will include naming accuracy and circumlocution attempts (i.e., naming attempts). Data from pre- and post-treatment spontaneous speech probes will include verbatim transcriptions of each participant's responses to the spontaneous speech probes (e.g., *Tell me all about your weekend*). Naming and spontaneous speech probe data will be collected

during the three pre-treatment and six post-treatment sessions. Audio recordings of naming probes will be randomized and coded for accuracy.

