b. Study endpoints. The participant's participation with the study will end when they request to withdraw from the study, or after the post-treatment assessments have been completed, whichever occurs first.

c. Statistical methods.

We will use visual inspection⁶⁸, mixed-effects modeling, and effect size calculations to analyze all results. For visual inspection, we will use the conservative dual-criterion method^{20,27,82}. We will use mixed-effects modeling to estimate the extent to which treatment-specific factors (fixed effects), pre-treatment cognitive-linguistic measures (random effects), and participant-specific factors (random effects) explain post-treatment naming and connected speech outcomes. We will calculate effect sizes by subtracting a participant's average pre-treatment score from their average post-treatment score and dividing by the pre-treatment standard deviation⁸.

Aim 1a. Measure PWAs' naming accuracy for trained and untrained objects. We will calculate effect sizes to measure the effect of treatment on participants' naming accuracy for trained objects, untrained semantically-related objects, and untrained semantically-unrelated objects between pre- and post-treatment. Hypotheses: Consistent with prior studies, we expect that naming treatment will yield medium to large effects for trained objects. Additionally, we hypothesize that strategy training will result in an increase in circumlocution-facilitated naming for untrained unrelated objects and yield medium effects for all untrained objects, regardless of semantic relatedness.

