Aim 1b. Determine whether PWA learn the strategy and consequently demonstrate a change in their language behavior in moments of naming difficulty. Analyses: We will use visual inspection to examine participants' identification of the strategy components from Treatment Week 2, to Week 8, to post-treatment sessions. We will calculate effect sizes to measure the effect of treatment on the total number of feature words produced during naming assessments and on the average number of feature words produced per naming attempt during assessments, from pre- to post-treatment. Hypotheses: We expect that strategy training will result in participants' ability to identify all six strategy components by Week 8 and at least four of the strategy components during maintenance/retention sessions. We also hypothesize that strategy training will lead PWA to produce more feature words (i.e., engage in circumlocution) during moments of naming difficulty. Specifically, we expect to find medium to large effects on the number of feature words PWA produce during naming attempts.

Aim 2. Evaluate the effect of strategy training on patients' language production during connected speech. Statistical Analyses: We will calculate effect sizes to measure the effect of treatment on number of object words, feature words, CIUs, and CIUs/minute participants produce during connected speech tasks. Hypotheses: We hypothesize that strategy training will lead PWA to produce more object and feature words during connected speech. We expect medium to large effects on object words, feature words, CIUs, and CIUs/minute during connected speech from pre- to post-treatment.

Additional analyses: We will create mixed-effects models using treatment-phase data (e.g., strategy component identification) as fixed effects, and pre-treatment cognitive-linguistic measures (e.g., CLQT+ results) and participant characteristics (e.g., aphasia severity) as random effects to further understand post-treatment outcomes. We will calculate normalized change scores to measure participants' overall improvement relative to their baseline performance and maximum possible change⁵⁶. We will report changes between participants' pre- and post-treatment WAB-R Aphasia Quotient⁴⁶ scores using the benchmarks proposed by Gilmore and colleagues³³.

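### Aim 2 takes object and feature words only as counts from speech samples of unfixed length, so a rise in them cannot be told apart from a longer sample

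*Combined protocol and SAP*

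**What the plan says.** Section VI.c, Aim 2, plans effect sizes for the "number of object words, feature words, CIUs, and CIUs/minute participants produce during connected speech tasks". The hypothesis there is that object and feature words will increase. Medium to large effects are expected on all four outcomes, with no numeric benchmark. The effect size, also in VI.c, is the participant's mean post-treatment score minus the mean pre-treatment score, "dividing by the pre-treatment standard deviation". Sample length does not enter it, and it is not named in the planned visual inspection or mixed-effects models either.

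On elicitation, V.a sets one connected speech probe at each baseline and each retention session. The prompt is open. Phase 1 joins picture, weekly activity and personal memory with an and/or, and Phase 4 joins them with an or. No time limit, word limit or stopping rule is given. The only nearby duration is the 30 minutes for the weekly assessment during treatment, which covers three different probes together.

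V.a (Phase 1) says that CIU analysis yields measures of both efficiency and informativeness, and I.c names both as targets. VI.a lists the verbatim responses but neither their duration nor the total words. Under IV.c everyone receives the same treatment, so there is no comparison arm.

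For Aim 1b, VI.c plans effect sizes on "the total number of feature words produced during naming assessments and on the average number of feature words produced per naming attempt during assessments".

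**The concern.** A count from a sample of unfixed length reflects two things: how densely the words occur and how long the person spoke. Treatment could change the second by itself. Step (f) of the treatment session urges participants to give as many features as possible, so longer answers after treatment are foreseeable. Familiarity with the task could have the same effect, and no untreated group shows how far sample length drifts without treatment.

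The rationale in I.c is about how speaking time is used: less of it spent searching for words, more of it carrying information. CIUs/minute addresses efficiency for CIUs. Object and feature words are the two outcomes named in the Aim 2 hypothesis, and feature words are the behaviour being trained, yet neither has a rate. If their counts rise, the planned analysis cannot say whether these words became more frequent in speech or the participant simply spoke for longer.

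**Working it through.** **Plan's own figure.** There is none to reproduce. The document gives no sample durations, word rates, baseline SDs or numeric meaning for medium and large. The goal of ten complete participants in VI.d has no effect size or SD behind it and plays no part here.

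**Inputs from the document.** Three counts and one rate (VI.c, Aim 2); d = (mean post − mean pre) / SD pre (VI.c); three pre-treatment and six post-treatment sessions (V.e). Because d uses session averages, having more post-treatment sessions does not itself inflate the counts.

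**Assumptions.** Words per minute do not change; mean speaking time rises by a fraction g; CV is the baseline SD of the count divided by its baseline mean.

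**Formula.** Mean post = (1 + g) × mean pre, so the numerator is g × mean pre. The denominator is CV × mean pre. Hence d(count) = g / CV. For any per-minute rate the numerator is zero, so d = 0 whenever the baseline SD of the rate is not zero.

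| Lengthening g | CV 10% | CV 20% | CV 30% | CV 40% |
|---|---|---|---|---|
| 10% | 1.00 | 0.50 | 0.33 | 0.25 |
| 25% | 2.50 | 1.25 | 0.83 | 0.625 |
| 50% | 5.00 | 2.50 | 1.67 | 1.25 |

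The three counts need not share one CV, so the same lengthening can give a different d on each.

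**Worked example (assumed values).** Baseline samples last 1.6, 2.0 and 2.4 minutes; post-treatment samples average 2.0 × 1.25 = 2.5 minutes. Rates stay at 6 object words, 4 feature words and 20 CIUs per minute.

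- Object words: 9.6, 12 and 14.4 before (mean 12, SD 2.4), 15 after; d = 3 / 2.4 = 1.25.
- Feature words: 6.4, 8 and 9.6 before (mean 8, SD 1.6), 10 after; d = 2 / 1.6 = 1.25.
- CIUs: 32, 40 and 48 before (mean 40, SD 8), 50 after; d = 10 / 8 = 1.25.
- CIUs/minute: 20 before and 50 / 2.5 = 20 after; no change.

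**Sampling check.** A simulation drew three pre-treatment and six post-treatment samples with lognormal durations, a constant rate and 200,000 runs. With talk 25% longer, the median d on a count was 1.54 at CV 20% and 1.06 at CV 30%, and d was positive in 95% and 86% of runs. With no lengthening, the median was 0.02 and 0.03. The medians exceed g / CV because an SD from three values often comes out too small.

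**What the planned outcomes already reveal.** CIUs divided by CIUs/minute gives the duration: 50 / 20 = 2.5 minutes. From that, object words per minute are 12 / 2.0 = 6 before and 15 / 2.5 = 6 after. The missing rate can therefore be derived from planned outcomes wherever CIUs are not zero, but VI.c does not plan to derive it.

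**The case against.** The strongest reply is that the counts measure exactly what is hypothesised. The plan predicts more object and feature words, and for a person with aphasia more talk may itself be a gain. The plan nowhere says that counts will be read as density or efficiency; CIUs/minute is there for efficiency. A participant who only talks longer would show rising counts with flat CIUs/minute, and a careful reader would notice. Elicitation is also not wholly loose, since one probe per session is set. The CIU method follows a published system that may standardise more than the document shows.

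Much of this stands. The counts are legitimate outcomes and should stay, and CIUs/minute does give a partial warning. But it speaks for CIUs, not for object or feature words, whose density could move differently. That duration can be recovered shows the remedy is cheap; it does not put the rate into the analysis.

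A reader might also infer that efficient participants will speak more briefly and so show falling counts. The document does not support that as the expected course: I.c predicts that speaking time will be used differently, not that samples will shorten.

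On Aim 1b, a reader might infer that the average per attempt has no meaning, or that its sign is open to choice. That goes too far. VI.c moves from "produce more feature words (i.e., engage in circumlocution) during moments of naming difficulty" straight to "the number of feature words PWA produce during naming attempts", and V.a and VI.a tie attempts to what is said before naming. V.e, with "circumlocution attempts (i.e., naming attempts", leans towards circumlocution episodes but sets no counting rule. Dividing by all 176 items is implausible: a constant divisor cancels from d, so the average would merely duplicate the total.

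**Conclusion.** The point holds for Aim 2 in a limited form. Object and feature words are analysed only as counts from samples whose length is not fixed, with no length adjustment and no comparison arm, so a rise cannot be told apart from longer talk. The direction of the effect needs only a longer sample at constant rates. Its size rests wholly on assumed lengthening and CV: 0.25 to 5.00 across the range shown, against no change on a rate.

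The document does not support the stronger conclusion that the Aim 2 counts are wrong outcomes or that the data would be unusable. The counts answer the hypothesis as worded, and transcripts and timing allow the gap to be closed before analysis. It should be closed, because Aim 2 is where the plan tests whether the strategy carries over into connected speech. The Aim 1b counting rule is a minor clarification and does not carry this point.

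**What to change.** In VI.c, Aim 2:

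- Keep the four planned outcomes.
- Add object words per minute and feature words per minute, with the same effect size, to be read beside the counts.
- Add percent CIUs (CIUs as a share of all words spoken) as a supporting measure of informativeness.
- State that a rise in counts without a rise in the rates will be reported as more talk, not as denser or more efficient speech.

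In VI.a, list sample duration and total words for each connected speech probe. As a minor addition for Aim 1b, fix before analysis what counts as one naming attempt.

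The cost is a few sentences, plus tabulation from transcripts and the timings that CIUs/minute already needs. There are two drawbacks. A few more measures will be reported on about ten completers. Timings may also be missing for participants who decline recording, as IV.b allows, a gap that CIUs/minute shares.

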During treatment data: During treatment, we will collect treatment session data and weekly probe data. Weekly probe data will be the exact same as the pre- and post-treatment naming and spontaneous speech probe data (naming accuracy, circumlocution attempts, verbatim transcriptions), in addition to strategy knowledge data probes (i.e., asking participants to identify as many of the six strategy components as possible). These weekly probes will occur once per week for the eight weeks of treatment. During the Strategy Education section of treatment, data will include quantification of strategy component knowledge (out of a possible six). During the Naming Treatment Plus Strategy Application section of treatment, data will include: Percent of items participant correctly identified whether they would be able to name the object before attempting to name it, naming accuracy before feature generation, number of features generated by the participant per item, number of correctly matched features with feature types per item, number of additionally identified feature types per item, and naming accuracy after feature generation. During the Strategy Debrief section of treatment, data will include: transcription of participant's reaction and opinion of treatment session and number of home-based opportunities identified by the participant in which they could use the strategy.

VI. BIOSTATISTICAL ANALYSIS

a. Specific data variables being collected for the study.

Cognitive-linguistic assessments (pre-treatment and post-treatment): Language and cognitive assessments will be scored based on standardized norms and methods of administration and scoring provided in testing manuals. Cognitive-linguistic assessments and inperson treatment sessions will be videotaped to provide a measure of reliability of scoring and administration of assessments and treatment.

Naming, spontaneous speech, and strategy knowledge probes (pre-treatment, during treatment, and post-treatment): We will collect (1) naming accuracy, (2) verbatim pre-naming verbal naming attempts, (3) verbatim responses to spontaneous speech probes, and (4) number of identified strategy components.

Treatment data: We will collect data on: (1) number of identified strategy components and (2) number of feature words during moments of naming difficulty.

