d. Power analysis (sample size, evaluable subjects). We will recruit 20 PWA subsequent to single left-hemisphere stroke with the goal of collecting complete data on ten participants, which is adequate for single-subject design^{68,69}.

VII. RISKS AND DISCOMFORTS

a. Complications of surgical and non-surgical procedures. Language and cognitive assessments and therapy tasks are noninvasive and pose no medical risks. Participants may experience some frustration during the course of the study, however, this frustration is not expected to be more than that what would be faced in situations requiring focused, sustained

attention for learning. A researcher will be present to answer any questions or concerns participants might experience.

All materials (history forms, data obtained during behavioral tasks) are for research purposes only and will be kept in confidence. Forms containing personally identifying information (history forms and data collected during cognitive-linguistic assessments) will be kept in a locked filing cabinet at the MGH IHP to which only the PI and approved study staff have access.

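### With baseline scores and aphasia severity entered as random effects, the secondary mixed model on its two usual readings returns only a variance and does not estimate how far they explain outcomes

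*Combined protocol and SAP*

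**What the plan says.** The opening paragraph of VI.c (Statistical methods) gives the purpose of the mixed models. They are to "estimate the extent to which treatment-specific factors (fixed effects), pre-treatment cognitive-linguistic measures (random effects), and participant-specific factors (random effects) explain" naming and connected-speech results after treatment. The Additional analyses paragraph of the same section repeats the allocation with examples: treatment-phase data are fixed, with "pre-treatment cognitive-linguistic measures (e.g., CLQT+ results) and participant characteristics (e.g., aphasia severity) as random effects".

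The two sentences agree, so this is not a slip in one place. No section gives a model formula, enters these measures as fixed covariates, cuts them into categories, or names participant as the grouping factor. VI.a says "Language and cognitive assessments will be scored based on standardized norms", which points to numeric scores. The battery is given in the pre-treatment phase (V.a), so each baseline score is one value per participant. VI.d plans to recruit 20 "with the goal of collecting complete data on ten participants".

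**The concern.** A random effect describes how units vary around a common mean. A baseline score whose explanatory value is wanted is a predictor, and its contribution is normally a fixed coefficient. Declared as a random effect, a score that is constant within participant yields a variance. That variance may have nothing to do with the score.

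This is the only analysis the plan describes that relates baseline cognition and severity to outcome. If it is run as written, the output gives no estimate of how much outcome changes with CLQT+ or severity, no direction, and no uncertainty for either.

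**Working it through.** The plan gives no formula or result to reproduce, so the check is algebra plus illustrations.

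**Inputs.** From the documents: about ten complete participants (VI.d), one baseline score each (V.a), and probe data collected "during the three pre-treatment and six post-treatment sessions" (V.e), hence 10 participants x 6 observations. Assumed, because the documents give no slopes or SDs: outcome = 0.3 x treatment-phase predictor + 0.8 x standardised CLQT+ score, participant SD 0.7, residual SD 0.7. Fits are maximum likelihood unless stated otherwise.

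**Reading 1: the score is a grouping factor.** If all scores are distinct, the score indicator matrix Z is the participant indicator matrix. With two such terms, V = (s1^2 + s2^2) ZZ' + s^2 I, so only the sum of the variances is identified. The numerical values of the score do not appear.
- Grouping by participant, CLQT+, CLQT+ reversed in sign, or CLQT+ shuffled gave log-likelihood -73.427 and the same estimates each time.
- A second example (REML, participant SD 0.5, residual SD 1) gave variance 1.508 and log-likelihood -87.462 for original, reversed and permuted scores. As a fixed covariate the same three versions gave slopes of +1.221, -1.221 and +0.086.
- With a true slope of 0, over 25 data sets, the score term still received a mean variance of 0.215, against 0.209 for a plain participant intercept. The two are not exactly equal because scores in those runs were not all distinct.

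**Reading 2: the score is a by-participant random slope, with an intercept and no fixed slope.** For participant i, V_i = (t0^2 + t1^2 x_i^2) J + s^2 I, where J is a matrix of ones. The score enters as its square, so its sign cancels. If intercept and slope are correlated, a term 2c x_i is added, and changing the sign of c absorbs the reversal. The parameter t1^2 says how the spread of participants changes with distance from the score's zero; it does not say how their mean shifts.
- Uncorrelated: -71.992 for score and for minus-score, -73.125 shuffled. Correlated: -71.509 for both signs.
- So the scores can affect the fit. In 500 simulated data sets with true slope 0.8, a shuffled score fitted strictly better than the real one in about 14%, against 3.5% for a fixed covariate. At slope 0.4 the figures were 25% against 23%, with exact ties in a further 19% under reading 2. Ties apart, there is little difference at 0.4.

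**Reading 3: severity cut into bands (not stated in the plan).** Band variance is then separable from participant variance. With true values 0.64 and 0.49, the band variance was estimated as zero in 27% of 1,000 runs with three bands and 23% with four. The middle 95% of estimates ran from 0 to 1.87 and from 0 to 1.81.

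**Score as a fixed covariate with a participant intercept.** In the first example the coefficient was 0.71 (SE 0.21), and -0.71 with the score reversed. Between-participant variance fell from 0.77 to 0.31, and (0.77 - 0.31)/0.77 = 0.60. A 95% interval on 8 degrees of freedom is 0.71 +/- 2.306 x 0.21, or 0.23 to 1.19.

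**A conditional side effect.** Suppose a treatment-phase predictor is reduced to one value per participant, and severity enters only as a grouping factor. The predictor's coefficient is then not adjusted for severity. With both at unit SD, the expected bias is severity slope x correlation: from 0.25 x 0.3 = 0.075 to 1 x 0.7 = 0.70 over assumed ranges. With severity as a fixed covariate it was within 0.003 of zero in simulation.

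**The case against.** The stated purpose speaks of extent, not direction, and could be met by a share of variance. This does not rescue reading 1, where the variance is simply that between participants and cannot be credited to the score. Under reading 2 the fit does respond to the scores, but t1^2 is not a share explained by a shift in mean.

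A reader might infer that direction is lost altogether. It is not. The predicted participant effects can be correlated with the score afterwards. Under the first example's SDs, the standard error of the slope through participant means is sqrt((0.49 + 0.49/6)/10) = 0.239. The sign is then right with probability of about 95% at slope 0.4 (0.4/0.239 = 1.67) and over 99.9% at 0.8; 500-run simulations gave 97% and 100%. But this is a step outside the model, and the plan does not describe it. A single shrunken random coefficient would also carry a sign (+1.188, and -1.188 with the score reversed, in the second example). It is non-standard and not described either.

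Severity has no stated scale. If it were banded, predicted band effects would show direction (-1.02, -0.35 and +1.37 in the second example). Bands for severity would not help numeric CLQT+ scores.

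A reader might also infer that the treatment-phase estimates are biased. The documents do not support that: strategy knowledge is probed weekly (V.a, V.e), and nothing says it will be reduced to one value per participant.

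Finally, ten participants support little modelling of any kind. That limits precision under every specification and is no reason to keep this one.

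**Conclusion.** The concern holds for the two usual readings with numeric scores: following the plan's wording does not answer the question the plan sets. The absence of a coefficient and the invariance to sign follow from the model's structure and need no assumed values. The exact identity with a participant intercept does need distinct scores. The log-likelihoods, percentages and coefficients are illustrations on assumed inputs, and the bias range applies only to a predictor with one value per participant.

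The consequence is limited. VI.c opens by listing mixed models among the methods for all results, and a reader might infer that the main findings are at risk. They are not: Aims 1a, 1b and 2 are specified through effect sizes and visual inspection, which do not use this model, and the treatment-phase fixed effects remain estimable.

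**What to change.** In both VI.c sentences, move the baseline measures to the fixed part. Name one or two in advance, for example the WAB-R Aphasia Quotient (VI.c already uses the "pre- and post-treatment WAB-R Aphasia Quotient" scores) and one CLQT+ score, both taken before treatment. Keep a random intercept for participant, and add one for item if naming is modelled at item level. Write out the model formula. Report coefficients with confidence intervals, labelled exploratory.

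The cost is the wording of two sentences; the data and software stay the same. The drawback is precision: with about ten complete participants the intervals will be wide, and only one or two covariates can be examined at once.

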a. Methods of enrollment. We plan to enroll 20 individuals with aphasia in a single-subject design intervention study in which all participants receive the same intervention protocol.

b. Procedures for obtaining informed consent. Once interest in participating in the study is expressed, one of the co-investigators involved in this study will establish contact with potential participants over the phone or via email. The research project will be explained and interested persons will be invited to the research site to discuss the study. The purpose, procedures, possible benefits and risks of the study will be explained to all potential participants. Potential participants will also be instructed that they can withdraw from the experiment at any time.

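### Ten completers are justified only for single-subject inference, yet the plan also fits models across participants with no cap on predictors and with measured scores entered as random effects

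*Combined protocol and SAP*

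**What the plan says.** Section IV.a describes a "single-subject design intervention study in which all participants receive the same intervention protocol". Section VI.d, the power analysis, reads "We will recruit 20 PWA subsequent to single left-hemisphere stroke" and continues "with the goal of collecting complete data on ten participants, which is adequate for single-subject design". It gives no significance level, power, effect size or standard deviation.

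Section VI.c names mixed-effects modelling as one of three methods for all results, and states its purpose: "We will use mixed-effects modeling to estimate the extent to which treatment-specific factors (fixed effects), pre-treatment cognitive-linguistic measures (random effects), and participant-specific factors", the last of these also labelled random effects, are to explain post-treatment naming and connected speech. The paragraph on additional analyses repeats the plan: "We will create mixed-effects models using treatment-phase data (e.g., strategy component identification) as fixed effects", with "pre-treatment cognitive-linguistic measures (e.g., CLQT+ results) and participant characteristics (e.g., aphasia severity) as random effects". Each class of predictor is illustrated by one example. There is no closed list, limit per model, selection rule, multiplicity rule or sample-size statement for these models.

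**The concern.** The sample-size statement and the models answer different questions. Single-subject inference asks whether one person changed, and repeated baselines and probes supply its information. The models ask why some people end up better than others. Everyone receives the same protocol, so a pre-treatment battery score or a characteristic such as severity varies only between people. Scoring 176 objects, or adding sessions, does not raise the number of independent values of such a predictor above the number of participants.

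The text speaks of measures and characteristics in the plural, alongside treatment-phase data, so several predictors per model is the natural reading and nothing limits it. A model with several participant-level predictors and ten people will fit well whether or not any of them matters. The risk is that chance patterns are reported as factors explaining response to strategy training.

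A second fault lies in the same sentence. A measured score is a covariate and needs a coefficient. The natural random effect here is participant, as the grouping factor.

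**Working it through.** **The plan's own figure.** Ten completers cannot be re-derived, because VI.d gives no inputs. The only arithmetic link is 10/20 = 50% completion, which is inferred from the two numbers.

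**Inputs.** n = 10 (the goal in VI.d), with n = 20 as the upper bound (all recruits complete). The number of participant-level predictors, k, is not stated, so a range is shown. A two-sided 5% level is assumed.

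**1. Fit expected by chance.** For a participant-level least-squares model with k unrelated predictors, the expected R-squared is k/(n-1).

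| k | n = 10 | n = 20 |
|---|---|---|
| 1 | 1/9 = 11% | 1/19 = 5% |
| 2 | 2/9 = 22% | 2/19 = 11% |
| 3 | 3/9 = 33% | 3/19 = 16% |
| 4 | 4/9 = 44% | 4/19 = 21% |
| 5 | 5/9 = 56% | 5/19 = 26% |

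The 95th percentile with no real relation, from Beta(k/2, (n-1-k)/2), is 70% for k = 3 and 89% for k = 5 at n = 10. At n = 20 it is 38% and 51%.

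**2. A single predictor.** The critical correlation is t/sqrt(n-2+t²).

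- n = 10: t = 2.306 on 8 degrees of freedom, so 2.306/sqrt(8 + 5.318) = 0.63.
- n = 20: t = 2.101 on 18 degrees of freedom, so 2.101/sqrt(18 + 4.414) = 0.44.

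Power at n = 10, by simulation with bivariate normal data and 200,000 draws per value, is 33% at a true r of 0.50, 68% at 0.70 and 80% at 0.76. At n = 20, 80% is reached near r = 0.58. The closed-form Fisher z value, tanh[(1.960 + 0.842)/sqrt(n-3)], is a little more pessimistic: 0.79 at n = 10 and 0.59 at n = 20.

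An observed r of 0.50 with ten participants has a 95% interval of tanh(0.549 ± 1.960/sqrt(7)), that is -0.19 to 0.86.

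**3. Size of the candidate pool.** Section V.a (Phase 1) lists seven instruments. Section V.e lists eight quantitative treatment-phase measures: one of strategy knowledge, six from the application section and one count of home opportunities. That makes 7 + 8 = 15. Section VI.a names only two treatment variables; with the seven instruments and severity that makes 7 + 2 + 1 = 10. These are counts of data collected, not of predictors that the plan commits to a model.

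**4. Screening the pool one at a time.** If the candidates are independent and unrelated to the outcome, the chance of at least one result below 0.05 is 1 - 0.95^10 = 40% for ten candidates and 1 - 0.95^15 = 54% for 15. With an assumed pairwise correlation of 0.5, simulation at n = 10 (3,000 runs) gives about 32% and 40%.

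**The case against.** The strongest reply is that the plan does not specify the models behind these figures. It gives no model size, significance level, screening step or promise to report R-squared. Aims 1a, 1b and 2 rest on effect sizes and visual inspection, and the predictor models are described in detail only under additional analyses. Most of this stands, and it limits what can be claimed. In mitigation, VI.c also lists mixed models among the methods for all results, and nowhere calls them exploratory.

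A reader might infer that the plan commits to 15 predictors and that chance alone will explain most of the variance. The documents do not support that. Fifteen counts what is collected, and severity may simply be the WAB-R, already in the battery. With ten participants, a pre-specified model of one to four participant-level predictors has a chance R-squared of 11% to 44%. It passes one half at about five predictors together, or if the best two or more are picked from the pool (in simulation the best two give 58% to 59% from ten candidates and 66% to 67% from 15). The plan states neither.

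A reader might also infer that every predictor has one value per participant. That fails for the treatment-phase class: features are counted per item and strategy knowledge is probed weekly, so an item-level or weekly model can use within-participant information. The figures above do not apply to it.

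Finally, k/(n-1) is a least-squares result. If the random-effects wording were taken to mean shrinkage, the chance fit would be lower. The wording does not define such a model.

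**Conclusion.** The point holds in conditional form. VI.d supports ten completers for within-participant inference only, while VI.c plans models across participants with no limit on predictors and no size statement. Followed as written, with several baseline scores and characteristics together, such models would be overfitted.

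The size depends on two numbers that the plan leaves open. For three to five participant-level predictors, the R-squared expected by chance is 33% to 56% with ten completers and 16% to 26% with 20. A single predictor with ten completers is detectable with 80% power only if the true correlation is about 0.76. Screening 10 to 15 independent candidates would give at least one false positive in 40% to 54% of trials, and fewer if they are correlated.

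These figures assume participant-level predictors entered as ordinary regressors, normal data and a 5% level. The main effect-size and visual-inspection analyses for Aims 1 and 2 are not affected.

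**What to change.** In VI.c, limit participant-level predictors to one variable named in advance (for example, strategy components identified at the last weekly probe) plus the pre-treatment score of the outcome. Enter both as fixed effects with a random intercept for participant, in place of entering measured scores as random effects. Report every other predictor one at a time as exploratory, with an interval and without a significance claim or an overall R-squared. If a per-item or weekly treatment-phase model is intended, say so and state its unit of analysis.

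In VI.d, state that ten completers support within-participant inference only, and give the detectable correlation: about 0.76 for 80% power with a single predictor. Adjusting for the pre-treatment score costs one degree of freedom and raises the critical value from 0.63 to 2.365/sqrt(7 + 5.591) = 0.67.

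The change is SAP wording and needs no extra participants, visits or data. The price is fewer predictor claims and a less favourable sample-size statement. Even the single named predictor will have low power for moderate relations (33% at r = 0.50, before adjustment), so its interval should carry the interpretation.
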